### b. Secondary outcome variables.

Additional secondary platelet outcomes will include light transmission aggregometry (LTA) at 2 hours, and also time-averaged PRU using mixed effects models. Given we hypothesize fentanyl may impair platelet inhibition due to reduced gastrointestinal absorption of ticagrelor, we will also compare ticagrelor pharmacokinetics in both arms, as determined by the area under the curve of active metabolite by liquid chromatography mass spectrometry (at 0, 0.5, 1, 2, 4 and 24 hours). We will also determine the impact of fentanyl on myocardial injury, as measured by high-sensitivity Troponin-I in the serum. In all 300 patients consented, we will also compare patient reported pain among both groups using the visual analog scale and the numeric rating scale (NRS). (12) These simple to perform subjective assessments can measure clinically meaningful differences in pain (e.g. a difference of 30% on the NRS). (12)

|   | YES                      | NO                       | Collection Date and TIME          |
|---|--------------------------|--------------------------|-----------------------------------|
| Pre Procedure Blood – Hour 0
• Platelet Function
- Verify Now  |  |  |    /    /    |
| Intra Procedure Blood- Hour 0.5
• Pharmacokinetics
• Platelet Function
- Verify Now   |  |  |    /    /    |
| Intra Procedure Blood- Hour 1
• Pharmacokinetics
• Platelet Function
- Verify Now   |  |  |    /    /    |
| Post Procedure Blood – Hour 2
• Pharmacokinetics
• Platelet Function
- Verify Now
- ADP-based LTA
• High Sensitivity Troponin
• Pain by Self-Report (visual scale) |  |  |    /    /    |
| Post Procedure Blood – Hour 4
• Pharmacokinetics
• Platelet Function
- Verify Now
• High Sensitivity Troponin  |  |  |    /    /    |
| Post Procedure Blood – Hour 24
• Pharmacokinetics
• Platelet Function
- Verify Now  |  |  |    /    /    |

*c. Statistical plan including sample size justification and interim data analysis.*

Based on prior data , we anticipate a 2 hour PRU of ~230 (Standard Deviation of 25) among patients receiving 180 mg ticagrelor without opiate and estimate a conservative effect size of 20% increase in 2hr PRU among those who receive fentanyl . These calculations yield a sample size estimate of  $\leq 23$  subjects per group (approx. 50 total) to achieve 90% power (2 sided alpha 0.05). Accounting for drop out and unanticipated increases in 2hr PRU variability, and to provide power for subgroup analyses, we will accrue 70 patients who undergo DAPT loading in total. In all analyses a value of  $p < 0.05$  will be considered statistically significant.

*d. Early stopping rules.*

N/A

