### 1. Abstract

With potent analgesic properties, perceived hemodynamic benefits and limited alternatives, opiates are the analgesic mainstay for acute coronary syndrome (ACS) patients reporting peri-procedural pain or nitrate-resistant chest pain. However, large observational studies suggest that opiate administration during ACS may result in adverse cardiovascular outcomes. Complimenting this, a number of recent mechanistic studies have demonstrated delayed and attenuated effects of oral dual anti-platelet therapy (DAPT) on platelet inhibition endpoints among subjects receiving intravenous morphine. These studies support the hypothesis that morphine delays the gastrointestinal absorption of DAPT medications. However, no data exist on the impact of intravenous fentanyl, a systemic opioid analgesic routinely administered during percutaneous coronary intervention (PCI) procedures, on the platelet inhibition effects of DAPT. We hypothesize that, similar to morphine, fentanyl administered at the time of PCI will reduce and delay the effect of DAPT on platelet function. As such, the primary aim of this study is to test the impact of intravenous fentanyl on residual platelet reactivity by randomizing patients undergoing PCI to a strategy of peri-procedural benzodiazepine plus non-systemic local analgesia or to the current standard of benzodiazepine plus intravenous fentanyl. Our study will address a major gap in knowledge. PCI analgesia with fentanyl is often administered concurrently with loading doses of DAPT, particularly in ACS. Given the critical need for rapid and robust inhibition of platelet function during PCI, our research study has true potential to change clinical practice, particularly if we demonstrate reduced DAPT absorption and elevated residual platelet reactivity among patients receiving fentanyl during PCI. As such, this research could result in a paradigm shift in the analgesia management of PCI and have a profound impact on optimization of post-PCI cardiac outcomes.

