### 2. Objectives

**Primary Objective:** We will test the hypothesis that randomization to fentanyl will be associated with higher residual platelet reactivity, as determined by mean P2Y12 reactivity units (PRUs) at 2 hours, among persons undergoing PCI with IV fentanyl analgesia (as well as aspirin and ticagrelor), compared to subjects randomized to undergo PCI with non-systemic analgesia.

**Secondary Objective:** To test the hypothesis that fentanyl administered during PCI will adversely impact the pharmacokinetics of ticagrelor, as determined by the area under the curve of active metabolite measured using liquid chromatography tandem mass spectrometry.

[figure not shown]
**Secondary Objective:** To test for differences in patient reported pain scores and biomarkers of myocardial injury, comparing PCI patients randomized to peri-procedural benzodiazepine plus non-systemic local analgesia or to the current standard of benzodiazepine plus intravenous fentanyl.

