### 3. Background

[figure not shown]
Morphine has long played a central role in the management of ACS. However, a 2005 observational study suggested that patients receiving morphine for pain relief in ACS had worse outcomes. In this context, recent research demonstrates that intravenous morphine delays and inhibits the absorption of oral DAPT with resultant delay in the time to maximal platelet inhibition. Hobl *et al.* administered a loading dose of 600mg clopidogrel together with either placebo or 5mg morphine intravenously in a randomized, double-blind, cross-over mechanistic trial. Morphine injection delayed clopidogrel absorption ( $T_{max}$ : 105 vs. 83 min,  $p = 0.025$ ) and reduced the total exposure to its active metabolite by 34% ( $p = 0.001$ , **figure 1**). Morphine also resulted in higher residual platelet aggregation and delayed maximal inhibition of platelets by 2 hours ( $n = 24$ ;  $p < 0.001$ ). Similar results have recently been reported for subjects receiving ticagrelor. Morphine's association with emesis, inhibition of gastric emptying and reduced GI motility is hypothesised as the cause.

Delayed and reduced absorption of DAPT in ACS patients is likely to translate into worse cardiovascular outcomes because maximal inhibition of platelet function is necessary to treat intracoronary atherosclerotic plaque rupture and thrombosis, as well as to minimize the risk of in-stent thrombosis among patients who receive coronary stents at the time of PCI. In keeping with this, morphine has also recently been associated with suboptimal reperfusion after PCI in patients with ACS (**figure 2**). As a consequence, 2015 European guidelines now state, “*in ACS patients whose ischemic symptoms are not relieved by nitrates and beta-blockers, opiate administration is reasonable..., with the caveat that morphine may slow intestinal absorption of oral platelet inhibitors.*”

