#### 4. Study Procedures

##### a. Study design, including the sequence and timing of study procedures

This is an open-label randomized controlled trial. We will accrue 70 patients undergoing loading of oral DAPT (aspirin and ticagrelor 180mg [the latter only being administered if a stent procedure is necessary]) as part of routine clinical care. This may require that up to 300 patients will need to be approached for consent. The reason for this is that only about 1 in 4 patients who undergo left heart catheterization actually need DAPT loading for stent placement (many do not need stents) and it is impossible to know who these patients will be before the catheterization procedure is performed.

Consenting patients will be randomized, 1:1, to peri-procedural intravenous benzodiazepine plus non-systemic local analgesia or to the current standard of peri-procedural intravenous benzodiazepine plus intravenous fentanyl plus local analgesia (**figure**).

Peri-procedural analgesia is part of routine clinical care, thus, the primary research procedure in this study is the randomization to the type of analgesia (fentanyl vs. no fentanyl).

Subsequent to randomization, clinical care will then proceed as per normal practice (e.g. patients requiring coronary stenting will undergo the procedure at the discretion of the interventional cardiologist). However, because ticagrelor is a newer DAPT option and is less commonly given at our hospital than clopidogrel, we will require that patients enrolled into our study not be switched from ticagrelor to clopidogrel within the first 12 hours of the initial ticagrelor load in the catheterization lab (this is due to theoretical concerns that clopidogrel loading is less effective

within the first 12 hours of ticagrelor loading due to competition for platelet receptors). As such, we require all patients enrolled into the study to be admitted for observation for 12-24 hours after enrolment. Ticagrelor was chosen for this study as it is a potent and fast-acting agent, has been demonstrated to be superior to clopidogrel, and will allow us to answer the main research question as to whether, or not, fentanyl delays the GI absorption of oral anti-platelet agents.

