In order to address our research objectives, enrolled patients will need to undergo sampling of blood after randomization (**figure**). While such blood sampling is typical in routine clinical care, we will also be obtaining blood for the sole purposes of research. Blood will be sampled at 0, 0.5, 1, 2, 4, and 24 hours after randomization. Where possible, blood will be drawn from existing IV access. For research purposes, we will also obtain patient-reported procedural pain data using the visual analog scale and the numeric rating scale at 2 hours (NRS).

*b. Study duration and number of study visits required of research participants.*

The duration of the study will be over 24 hours. The only study visit required is the admission during which the PCI is being performed as part of routine clinical care. Of note, patients undergoing PCI are routinely kept in the hospital for a minimal of 24 hours.

*c. Blinding, including justification for blinding or not blinding the trial, if applicable.*

Patients will not be blinded to the analgesia strategy (benzodiazepine sedation and local vs systemic analgesia) as the coronary angiogram is being performed as part of routine clinical care and it will not be possible to blind medical providers to the medications administered during the procedure. However, the collaborators who perform the analyses of blood samples will be blinded to the randomized allocation in order to minimize ascertainment bias.

*d. Justification of why participants will not receive routine care or will have current therapy stopped.*

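### The only PK outcome, one metabolite AUC on draws to 24 h, says little about delayed absorption, and the time-averaged PRU has no stated window, weights or baseline handling

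*Combined protocol and SAP*

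**What the plan says.** **PK outcome.** Section 2 sets out to test whether fentanyl will "adversely impact the pharmacokinetics of ticagrelor, as determined by the area under the curve of active metabolite". Section 7b repeats this single summary: "area under the curve of active metabolite by liquid chromatography mass spectrometry (at 0, 0.5, 1, 2, 4 and 24 hours"). No Tmax, Cmax, partial AUC, AUC window or calculation rule appears anywhere.

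**Hypotheses.** Section 7b ties the AUC to reduced absorption. The abstract expects that "fentanyl administered at the time of PCI will reduce and delay the effect of DAPT on platelet function". Section 4a gives the main research question as whether "fentanyl delays the GI absorption of oral anti-platelet agents".

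**Prior evidence.** Section 3 cites a morphine-clopidogrel trial that reported timing and extent separately: Tmax 105 against 83 minutes, and morphine "reduced the total exposure to its active metabolite by 34" per cent. It also "delayed maximal inhibition of platelets by 2 hours".

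**Clock.** Section 4a says: "Blood will be sampled at 0, 0.5, 1, 2, 4, and 24 hours after randomization". The same section describes ticagrelor as "the latter only being administered if a stent procedure is necessary".

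**PRU.** Section 7a lists six VerifyNow times and makes 2 h the primary outcome. Section 7b adds a time-averaged PRU from mixed effects models and says nothing about window, weights, baseline or model terms.

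**The concern.** Delay and loss of extent are different findings, and the plan's own background treats them separately. One AUC over 24 h cannot tell them apart. A short delay leaves it almost unchanged, so a null result could hide the effect that section 4a asks about. A long delay lowers the level at the 4 h draw and, on so sparse a schedule, can look like lost exposure. The PK objective is there to explain mechanism, so this is where the distinction matters.

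Two features make it harder. Draws are timed from randomization but the load comes later, so nominal hours are not hours since the load, and early draws may precede it. Section 8a also implies that a further ticagrelor dose can fall due before the 24 h draw.

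For the time-averaged PRU, different reasonable averages of the same readings give very different power, and the plan does not choose among them.

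**Working it through.** The plan gives no figure for either outcome, so there is none to reproduce. Its sample size concerns 2 h PRU only.

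**1. Trapezoid weights** (draw times from section 7b). Each draw gets half of the interval on either side:

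| Draw (h) | 0 | 0.5 | 1 | 2 | 4 | 24 |
|---|---|---|---|---|---|---|
| Weight (h) | 0.25 | 0.5 | 0.75 | 1.5 | 11 | 10 |

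The sum is 24. The last two draws carry (11 + 10)/24 = 87.5%; the 0.5, 1 and 2 h draws together carry 2.75/24 = 11.5%.

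**2. Effect of a pure delay.** Assumed model, load at hour 0, no second dose: C(t) = ka/(ka - k) x (exp(-kt) - exp(-ka t)), with k = ln 2/half-life, ka 0.5-2/h and half-life 6-12 h. The documents give no kinetics. A delay shifts the curve to the right. The 22 minutes is 105 - 83 from section 3. The 1 h and 2 h delays are illustrative; section 3's 2 h refers to platelet inhibition, not concentration. Ratios are delayed over undelayed:

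| Delay | Sparse AUC(0-24 h) | True AUC(0-24 h) | AUC(0-4 h) |
|---|---|---|---|
| 22 min | 0.974-1.009 | 0.992-0.997 | 0.868-0.920 |
| 1 h | 0.915-1.002 | 0.977-0.991 | 0.627-0.694 |
| 2 h | 0.780-0.974 | 0.952-0.982 | 0.290-0.305 |

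One cell worked: ka 0.5/h, half-life 8 h. Undelayed levels at the six draws are 0, 0.216, 0.376, 0.572, 0.692 and 0.151, and the weighted sum is 10.37. With a 2 h delay only the last two are non-zero, 0.572 and 0.180: 11 x 0.572 + 10 x 0.180 = 8.09. The ratio is 8.09/10.37 = 0.78.

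**3. What an early AUC does and does not show.** A uniform 34% loss multiplies both AUCs by 0.66. The early AUC therefore responds to lost extent as well as to delay.

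**4. The ratio early AUC/AUC(0-24 h).** Let A and B be the contributions of the load and of a second dose to AUC(0-24 h). If a 34% loss affects the load only, the between-arm ratio of ratios is 0.66 x (A + B)/(0.66A + B). With B = 0 this is 1. With a second dose at 12 h of half the load it is about 0.91-0.94, and with one equal to the load about 0.86-0.90. Pure loss of extent would then look like delay.

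**5. Time-averaged PRU.** From section 7c: effect 0.20 x 230 = 46, SD 25, 35 per arm. Assumed: the average has the SD of one reading, and there is no effect at 0 or 24 h. The standard error is 25 x sqrt(2/35) = 5.98; power is for a two-sided t-test at 0.05. For an effect from 0.5 h that is gone by 4 h:

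- six-visit mean: 3 x 46/6 = 23.0, power 97%
- time-weighted 0-24 h: 2.75 x 46/24 = 5.27, power 14%
- mean of the 0.5-4 h draws: 3 x 46/4 = 34.5, power above 99.9%

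If the effect is still full at 4 h, the three powers are 99.9%, 99% and above 99.9%.

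If the load is at 1 h and the effect starts at 2 h, the shares of the effect kept are 17%, 6% and 25% when it is gone by 4 h (power 24%, 8% and 48%). When it is full at 4 h they are 33%, 52% and 50% (power 72%, 98% and 97%).

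**The case against.** AUC is the right summary for the reduced-absorption hypothesis attached to it in section 7b. Delay is also addressed by 2 h PRU, 2 h LTA and the serial PRU readings. Both points stand. A reader might infer that the AUC is the wrong endpoint or that the trial cannot detect delay, and the documents support neither. The gap is that the PK objective alone cannot separate delay from lost extent.

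The kinetics are assumed, and the long-delay case is weakly anchored. The only concentration-based delay in section 3 is 22 minutes, and that barely moves AUC(0-24 h). The 22% fall needs absorption at 0.5/h; at 1-2/h a 2 h delay lowers it by 3-13%. This stands as a limit on size. The 87.5% weight needs no kinetics, only the linear rule.

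A reader might also infer that a lower early/0-24 h ratio proves delay. Step 4 shows that it does not once a second dose precedes the 24 h draw.

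Nor does section 7a's list of times define a six-visit mean, and nothing suggests that the averaging rule is meant to be chosen after seeing the data. The plan is simply silent.

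**Conclusion.** The point holds as a specification gap in secondary outcomes that should be closed. AUC(0-24 h) is nearly blind to delays of 22 minutes to 1 h (-9 to +1%), whereas AUC(0-4 h) falls by 8-37%. A 2 h delay, if it occurred, would lower the sparse AUC(0-24 h) by 3-22% against a true fall of 2-5%. These figures rest on the assumed one-compartment range, a load at hour 0 and the linear trapezoid.

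The time-averaged PRU is undefined, and the choice of average can move power from 14% to above 99.9% on section 7c's inputs under the stated effect pattern. The primary 2 h PRU and the 2 h LTA are not affected.

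**What to change.** 1. **Early exposure.** Add a partial AUC from the ticagrelor load to one fixed post-load time that the 4 h draw reaches, on actual times since load. Fix the window before concentrations are released, from load and draw times pooled over arms, and say how a draw that falls short is handled. Record the clock time of the load, which the documents do not list as collected. Call the result early exposure, not a test of delay. If the latest load is 1 h after randomization (assumed), the window is 3 h with two to four post-load draws up to the 4 h draw.
2. **AUC(0-24 h).** Keep it, state its calculation rule, and flag 24 h values taken after a further ticagrelor dose or a switch.
3. **Ratio.** Use early AUC/AUC(0-24 h) only descriptively, in patients with no further ticagrelor dose or switch before the 24 h draw. Use the raw scale or ranks, because the early AUC can be zero.
4. **PRU.** Fit the mixed model to post-baseline draws through 4 h, with hour-0 PRU as covariate and an arm-by-time term. Report the equal-visit average difference, report 24 h separately, and add a sensitivity analysis by time since load.
5. **Minor documentation.** Section 7b's text lists PK at hour 0 but its collection form does not. Sections 4a (12-24 h observation, 12 h bar on switching), 4b (24 h study and stay) and 8a (switching after study completion) leave unclear whether discharge or a switch can precede the 24 h draw. These passages must be reconciled.

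**Cost.** No new samples; one or two more secondary results to report. Late loads leave fewer draws in the early window. If the load is at 1 h and the effect lasts to 4 h, the 0.5-4 h mean does no better than a time-weighted one (50% against 52% of the effect kept).

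### Troponin is assayed only at Hours 2 and 4, although blood is also drawn at Hours 0 and 24, so myocardial injury that shows after Hour 4 can be missed

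*Combined protocol and SAP*

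**What the plan says.** Section 2 of the combined protocol and SAP includes this secondary objective: "To test for differences in patient reported pain scores and biomarkers of myocardial injury". Section 7.b names the marker: "We will also determine the impact of fentanyl on myocardial injury, as measured by high-sensitivity Troponin-I in the serum". Neither section gives a troponin time point, summary measure or test, and the statistical plan in section 7.c adds none.

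Section 4.a sets the draws: "Blood will be sampled at 0, 0.5, 1, 2, 4, and 24 hours after randomization". The collection table in section 7.b assigns assays to those draws. Troponin appears in the row headed "Post Procedure Blood – Hour 2" and in the Hour 4 row, and nowhere else. The row headed "Post Procedure Blood – Hour 24" lists pharmacokinetics and VerifyNow. The Hour 0 row, labelled pre-procedure, lists VerifyNow only. The documents give no reason for leaving troponin out of either row.

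**The concern.** The trial's reasoning runs from fentanyl, through delayed or weaker platelet inhibition, to worse myocardial outcome. Section 3 links delayed absorption to thrombosis and in-stent thrombosis and puts no upper time limit on those events. A sample at Hour 4 cannot show injury, or release of troponin from earlier injury, that comes after it. If the arms show no difference at Hours 2 and 4, the trial could not tell an absence of effect from an effect that had yet to appear in the blood.

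There is a second gap in the same table. Without an Hour 0 troponin, elevation present before the procedure cannot be separated from procedural injury or adjusted for. Section 5 does not exclude patients whose troponin is already raised, and the protocol is motivated largely by acute coronary syndromes.

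**Working it through.** The documents state no sample size, power or effect size for troponin, so there is no plan figure to reproduce. The check is a reading of the table followed by time arithmetic.

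**Step 1: the table, row by row (section 7.b; hours counted from randomisation, section 4.a).**

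| Draw | Table label | Troponin listed |
|---|---|---|
| Hour 0 | pre-procedure | no |
| Hour 0.5 | intra-procedure | no |
| Hour 1 | intra-procedure | no |
| Hour 2 | post-procedure | yes |
| Hour 4 | post-procedure | yes |
| Hour 24 | post-procedure | no |

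**Step 2: when the procedure ends.** One row is headed "Intra Procedure Blood- Hour 1" and the next "Post Procedure Blood – Hour 2". Taking the labels at face value, the end time E lies between 1 and 2 hours after randomisation.

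**Step 3: time from the end of the procedure to each draw (draw time minus E).**

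- Last troponin: 4 − 2 = 2 h to 4 − 1 = 3 h.
- Hour 24 draw: 24 − 2 = 22 h to 24 − 1 = 23 h.
- Period after the last troponin: 24 − 4 = 20 of the 24 study hours.

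**Step 4: what the outcome should be compared with.** Let d0, d2 and d24 be the true differences between arms in log troponin at Hours 0, 2 and 24.

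- Change from Hour 2 to Hour 24 estimates d24 − d2. Hour 2 follows randomisation and the procedure, so d2 may already carry a treatment effect, and subtracting it removes part of what the trial is looking for.
- Change from Hour 0, or adjustment for Hour 0, targets d24, because d0 = 0 apart from chance. This assumes that the Hour 0 blood is taken before any study analgesia, as its pre-procedure label implies, and that allocation does not influence who is stented and loaded.

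Only the Hour 0 value is therefore a sound baseline.

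**Step 5: cost in assays.** Section 7.c accrues 70 loaded patients. One added time point is 70 × 1 = 70 assays, and two are 70 × 2 = 140, beside the 70 × 2 = 140 already planned.

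**The case against.** The strongest reply is that the sampling fits the mechanism. If fentanyl delays inhibition, its patients are less protected during the delay, which lies around stenting. Excess injury would then begin early, and two post-procedure samples are a reasonable way to look for it. Sections 2 and 7.b do not promise to measure late or total injury. This stands as far as it goes: the planned samples do address early peri-procedural injury. It does not show that Hour 4 is late enough. The documents give no troponin kinetics and no time limit on the thrombotic events they describe.

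Two practical objections also stand. Troponin is to be measured in serum, and no serum tube or stored aliquot is described at Hour 24, so a blood draw exists but a suitable sample may not. Section 4.a requires only 12 to 24 hours of observation, although section 4.b says that at least 24 hours is routine, so some 24-hour values may be missing.

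A reader might go further and infer that any effect must arise after the ticagrelor load plus a fixed delay, and then count the hours left before each sample. The documents do not support this. The under-inhibited period is the delay itself, not the time after it. The finding in section 3, "delayed maximal inhibition of platelets by 2 hours", comes from morphine with clopidogrel (n = 24) and describes time to maximal inhibition. For ticagrelor, section 3 says only that similar results were reported and gives no delay. The time from randomisation to the load is not stated either.

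**Conclusion.** The point holds as a limited, low-cost improvement. The last troponin comes about 2 to 3 hours after the procedure ends, and the remaining 20 of 24 study hours have no troponin value although blood is drawn at Hour 24. Injury or release after Hour 4 can be missed, and a null troponin result should be read as evidence about early peri-procedural injury only. The size of what is missed cannot be derived from the documents.

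The conclusion rests on the table's procedure labels. They are nominal, and a procedure that runs past Hour 2 in an individual patient would shorten the 2 to 3 hours.

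A reader might also infer that the secondary objective goes unanswered. That is too strong: it is answered for the early window, without a baseline and without a prespecified summary. The primary outcome is not affected.

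**What to change.** - In the section 7.b table, add high-sensitivity troponin to the Hour 24 row and to the Hour 0 row, and state that a serum tube is taken at both draws if the existing tubes do not yield serum.
- In section 7.b or 7.c, define the injury outcome as log troponin at 24 hours, compared between arms with adjustment for log troponin at Hour 0. Name Hours 2 and 4 as supporting times, analysed with the same adjustment. Do not use change from the Hour 2 value.
- Report the number of missing 24-hour values by arm.

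The cost is about 70 assays for each added time point, 140 for both, possibly one serum tube at each of two existing draws, and no new draw or visit. Section 4.a says that the need for a stent is not known before catheterisation, so Hour 0 serum would have to be kept from patients who later prove not to be loaded (up to 300 are to be approached). Assaying only the loaded patients keeps the Hour 0 count at about 70. The main downside is some missing 24-hour values among patients observed for less than 24 hours, for whom Hours 2 and 4 remain available.

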Treatment failure will be defined as subject-report of uncontrolled pain or discomfort during the PCI procedure. As part of routine care patients are regularly asked to report any pain during the procedure. In all instances, and most notably in the group randomized to initial intravenous benzodiazepine plus non-systemic analgesia, post randomization analgesia will be managed as per usual by the procedural team. Specifically, the study protocol only provides initial guidance on analgesia, based on the randomized allocation. Once the initial analgesia has been provided, should patients subsequently report uncontrolled pain or discomfort, the treating team can administer any analgesia that they feel is clinically indicated, including intravenous fentanyl in either arm of the study. There are no protocol-based removal criteria. However, participants can remove themselves at any time from the study as participation is voluntary.

g. *Description of what happens to participants receiving therapy when study ends or if a participant's participation in the study ends prematurely.*

When the study ends or should participation end prematurely, all subjects enrolled will undergo routine treatment as per usual best practice. Participants will be analyzed on an intention to treat basis. Therefore, participants will be analyzed based on their initial randomized analgesia allocation and whether or not their participation in the study ended prematurely.

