## 7. Study Statistics

### a. Primary outcome variable.

In both randomized groups P2Y12 reactivity units (PRUs), measured using VerifyNow, will be determined at 0, 0.5, 1, 2, 4, and 24 hours. The primary outcome will be mean PRU at 2 hours.

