## **8. Risks**

*a. Medical risks, listing all procedures, their major and minor risks and expected frequency.*

It is possible that the non-systemic analgesia arm could report increased peri-procedural pain, however IV opiates are permitted at any time, for any participant, based on *break-through pain reported* during the case. The other main medical risks are the bleeding and bruising from venipuncture. Where possible we will draw blood from IV access to minimize venipuncture. As our research protocol includes the administration of ticagrelor as the anti-platelet agent used for the stenting procedure, some providers may wish to transition their patients from ticagrelor to other anti-platelet agents (such as clopidogrel or prasugrel) after completion of participation in our study. This change may be motivated by clinical or patient preference reasons. However, if the provider elects to make such a change after the participant has completed the study, we will require them to not change to either clopidogrel (starting with a 600mg load) or prasugrel (starting with a 60mg load) within the first 12 hours of the initial ticagrelor load (specifically, they will need to wait until 12 hrs has passed from the last ticagrelor dose and then load with the alternative agent at the time the next dose of ticagrelor would have been due. This requirement will minimize the risk that patients who are switched from ticagrelor to an alternative anti-platelet agent will not be exposed to the potential risk of suboptimal platelet inhibition in the period around which this change is made.

*b. Steps taken to minimize the risks.*

As already mentioned, blood will be drawn from existing iv heparin locks when available. Furthermore, we plan to minimize difference in pain by applying effective non-systemic analgesia that will consist of a rigorous pain relief strategy of potent benzodiazepine and effective local anaesthetic (e.g. subcutaneous lidocaine). In addition, patients can request more pain relief (including opiates) after the initial randomized analgesia has been allocated and can withdraw at any time from the study.

*c. Plan for reporting unanticipated problems or study deviations.*

Any unanticipated problems will be reported to the IRB.

*d. Legal risks such as the risks that would be associated with breach of confidentiality.*

Date will be stored on a secure and encrypted P.I.'s computer.

*e. Financial risks to the participants.*

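### The printed inputs (2-hour PRU about 230, SD 25, 20% increase) need 8 patients per group for 90% power; the stated 23 per group, about 50 in total, does not follow from them.

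*Combined protocol and SAP*

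**What the plan says.** Section 7a of the combined protocol and SAP sets the endpoint: "The primary outcome will be mean PRU at 2 hours". Section 7c contains the whole sample-size argument, in this order.

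- Control arm: "we anticipate a 2 hour PRU of ~230 (Standard Deviation of 25) among patients receiving 180 mg ticagrelor without opiate".
- Effect: "estimate a conservative effect size of 20% increase in 2hr PRU among those who receive fentanyl".
- Result: "These calculations yield a sample size estimate of $\leq 23$ subjects per group (approx. 50 total) to achieve 90% power", with a two-sided alpha of 0.05.
- Only then the margin: "Accounting for drop out and unanticipated increases in 2hr PRU variability, and to provide power for subgroup analyses", the plan will accrue 70 patients who undergo DAPT loading.

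Allocation is 1:1 (section 4a). No test, formula, drop-out rate, named subgroup or other input is given.

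Two other provisions bear on the size of the difference to expect. Section 4f says that, once the initial analgesia has been given, "the treating team can administer any analgesia that they feel is clinically indicated, including intravenous fentanyl in either arm of the study", and section 8a repeats that "IV opiates are permitted at any time, for any participant". Section 4g says: "Participants will be analyzed on an intention to treat basis". The calculation in section 7c mentions neither rescue nor its effect.

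**The concern.** A 20% rise on 230 is 46 PRU, almost two standard deviations at SD 25. A difference that large needs very few patients, so 23 per group looks about three times too big for the inputs it is said to come from. Either an input that was used is not the one printed, or a margin was included that the text does not disclose.

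This is the only power statement for the primary outcome. A reader who cannot reproduce it cannot tell what variability the trial was sized for, or what a null result at 70 patients would rule out.

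**Working it through.** **Inputs.** Control mean 230 and SD 25; increase of 20%; power 90%; two-sided alpha 0.05 (all section 7c). Two groups, 1:1 (section 4a). Continuous endpoint, PRU at 2 hours (section 7a).

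**Step 1. Effect.** Difference = 0.20 × 230 = 46 PRU. Standardised difference d = 46/25 = 1.84.

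**Step 2. Size on the printed inputs.**

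- Normal approximation: n = 2(1.960 + 1.2816)² / 1.84² = 6.2, so 7 per group.
- Two-sample t-test (noncentral t): 7.3, so 8 per group. Power is 0.884 at 7 and 0.928 at 8.
- Total: 16, against about 50 stated.

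**Step 3. Power at the stated size.** At 23 per group with d = 1.84, power is 0.99998, not 0.90. The plan's figure is not reproduced.

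**Step 4. Other ordinary choices.** Each changes one thing from Step 2.

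| Change | Per group |
|---|---|
| One-sided test | 6 |
| 95% power | 9 |
| SD growing with the mean (25 and 30) | 9 |
| Log scale | 9 |
| Rank test, minimum asymptotic efficiency 0.864 | 9 (7.3/0.864 = 8.5) |
| Alpha 0.01 | 11 |
| 230 taken as the fentanyl-arm mean | 11 |
| 99% power | 12 |

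None approaches 23.

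**Step 5. Dilution by rescue.** The documents give no rescue rate. If the 46 PRU difference were 20% or 30% smaller (assumed), it would be 36.8 or 32.2 PRU. At SD 25 that needs 10.8 or 13.7, so 11 or 14 per group. This does not reach 23 either.

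**Step 6. What would give 23.** By t-test, 23 per group has 90% power at d = 0.977. That is 0.977 × 25 = 24.4 PRU at SD 25, or an SD of 46/0.977 = 47.1 for 46 PRU. These are back-solutions; the documents state neither.

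**Step 7. What 70 patients can do.** Drop-out is assumed at 0, 10% or 20%, because no rate is given: 70/2 = 35, 63/2 = 31.5 and 56/2 = 28 evaluable per group. The last three columns give the largest SD that keeps 90% power, with the full difference and with the two assumed reductions.

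| Evaluable per group | Detectable at SD 25, 90% power | 46 PRU | 36.8 PRU | 32.2 PRU |
|---|---|---|---|---|
| 35 | 19.7 PRU | SD 58.5 | SD 46.8 | SD 41.0 |
| 31.5 | 20.7 PRU | SD 55.4 | SD 44.3 | SD 38.8 |
| 28 | 22.1 PRU | SD 52.1 | SD 41.7 | SD 36.5 |

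At SD 25, power stays above 99% throughout. The lowest value is 0.997, with 32.2 PRU and 28 per group.

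**The case against.** The strongest reply is that nothing here is literally false. The plan says at most 23, and 8 is at most 23. Twice 23 is 46, so about 50 is only the rounded total of that ceiling and not a second discrepancy. The error, if it is one, runs in the safe direction, and the plan gives its reasons for the 70 it adopts.

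Much of that stands: the bound is true, the direction is conservative and no patient is affected. But the plan presents the figure as what its inputs produce, then builds from about 50 to 70. A bound nearly three times the requirement, used as the working number, is not a derivation.

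A second reply is that rescue is a separate issue: it does not explain 23, no rate is documented, and extra fentanyl in the fentanyl arm is not crossover. This is fair. The contrast shrinks mainly through opiate use in the non-systemic arm. Dilution matters here only because any statement of what 70 can detect should say whether it allows for it.

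A third reply is that reassurance about 70 depends on which number is wrong. This is partly right. If the SD actually used was near 47, 70 patients still keep 90% power for an undiluted 46 PRU with 20% loss (limit about 52). They would not keep it with a 20% smaller difference and 20% loss (limit about 42). The documents support neither that SD nor those rates, so this is a reason to disclose the derivation and not evidence that the trial is too small.

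**Conclusion.** The point holds, as a minor one. The printed inputs require 8 per group, 16 in total, and not 23 per group or about 50. The result rests on a two-sample t-test with equal SD, and every ordinary variant tried gives 12 or fewer. Why 23 was written is not shown, and no cause is asserted here. On the printed inputs the trial is larger than it needs to be, and there is no sign that it is underpowered. The drop-out and dilution figures above rest on assumed rates.

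**What to change.** Keep 70, and restate the paragraph in section 7c so that the size follows from its inputs. The sponsor should first check which inputs were used, then take one of two routes.

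1. If the printed inputs are the intended ones, give their result and justify 70 by what it can detect. Possible wording:

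> For a 2-hour PRU of 230, an SD of 25 and a 20% (46 PRU) increase, a two-sample t-test at two-sided 0.05 needs 8 per group for 90% power. We will accrue 70. With 35 per group evaluable, this has 90% power for 20 PRU at SD 25, or for 46 PRU at an SD up to about 58. With an assumed 10–20% loss, it has 90% power for 21–22 PRU at SD 25, or for 46 PRU at an SD up to about 52–55. These figures do not allow for dilution of the difference by permitted opiate rescue under intention to treat.

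   The sponsor should replace the assumed loss with its own figure if it has one. Subgroup analyses can remain as a reason for the margin, but the plan gives no subgroup or difference from which their power could be worked out.

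2. If other inputs gave 23, state that SD, difference and test, and restate from them what 70 can detect.

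The cost is wording in one paragraph. Accrual, procedures and analyses do not change.
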